XXX	XXX	XXXXXXXX	DDMMYYYY	DDMMYYYY	X	XXX	XXX	XXX
XXX	XXX	XXXXXXXX	DDMMYYYY	DDMMYYYY	X	XXX	XXX	XXX

Source: XXXX.SAS, Run on DDMMYYYY

Listing 52) Total progression free survival, 3-years PFS and BORR

POPULATION: ITT

Treatment Arm	Site	Patient Number	Date of randomization (DDMMYYYY)	Date of second progression / last contact date (DDMMYYYY)	Censoring (0=censored, 1=event)	Total PFS (months)	3-years PFS (Yes/No)	BORR
XXX	XXX	XXXXXXXX X	DDMMYYYY	DDMMYYYY	X	XXX	XXX	XXX
XXX	XXX	XXXXXXXX X	DDMMYYYY	DDMMYYYY	X	XXX	XXX	XXX
XXX	XXX	XXXXXXXX X	DDMMYYYY	DDMMYYYY	X	XXX	XXX	XXX
XXX	XXX	XXXXXXXX X	DDMMYYYY	DDMMYYYY	X	XXX	XXX	XXX
XXX	XXX	XXXXXXXX X	DDMMYYYY	DDMMYYYY	X	XXX	XXX	XXX
XXX	XXX	XXXXXXXX X	DDMMYYYY	DDMMYYYY	X	XXX	XXX	XXX
XXX	XXX	XXXXXXXX X	DDMMYYYY	DDMMYYYY	X	XXX	XXX	XXX
XXX	XXX	XXXXXXXX X	DDMMYYYY	DDMMYYYY	X	XXX	XXX	XXX

Source: XXXX.SAS, Run on DDMMYYYY

Listing 53) Duration of Response (DoR)

POPULATION: ITT

Treatment Arm	Site	Patient Number	Date of first documented response (CR or PR) (DDMMYYYY)	Date of first progression or death du to cancer / last tumor assessment date (DDMMYYYY)	Censoring (0=censored, 1=event)	DoR (months)
XXX	XXX	XXXXXXXX	DDMMYYYY	DDMMYYYY	X	XXX
XXX	XXX	XXXXXXXX	DDMMYYYY	DDMMYYYY	X	XXX
XXX	XXX	XXXXXXXX	DDMMYYYY	DDMMYYYY	X	XXX
XXX	XXX	XXXXXXXX	DDMMYYYY	DDMMYYYY	X	XXX
XXX	XXX	XXXXXXXX	DDMMYYYY	DDMMYYYY	X	XXX
XXX	XXX	XXXXXXXX	DDMMYYYY	DDMMYYYY	X	XXX
XXX	XXX	XXXXXXXX	DDMMYYYY	DDMMYYYY	X	XXX

Source: XXXX.SAS, Run on DDMMYYYY

Listing 54) Adverse events

POPULATION: SAF

Patient Number	AE#	Date on which the investigator finds out of the event (DDMMYYYY)	Description of event	Preferred Term	SOC	Start Date (DDMMYYYY) / End Date (DDMMYYYY)	Causality	Ongoing?	Related to	SAE	AESI	Grade	Outcome	Action taken	Trt. Req.?
XXXXX	X	DDMONYYYY	XXXXXX	XXXXXXXXXX	XXXXXXXXXX	DDMONYYYY / DDMONYYYY	XXXXXX	XXXXXX	XXXXXX	X	X	xxx	xxx	xxx	xxx
	X	DDMONYYYY	XXXXXX	XXXXXXXXXX	XXXXXXXXXX	DDMONYYYY / DDMONYYYY	XXXXXX	XXXXXX	XXXXXX	X	X	xxx	xxx	xxx	xxx
	X	DDMONYYYY	XXXXXX	XXXXXXXXXX	XXXXXXXXXX	DDMONYYYY / DDMONYYYY	XXXXXX	XXXXXX	XXXXXX	X	X	xxx	xxx	xxx	xxx
	X	DDMONYYYY	XXXXXX	XXXXXXXXXX	XXXXXXXXXX	DDMONYYYY / DDMONYYYY	XXXXXX	XXXXXX	XXXXXX	X	X	xxx	xxx	xxx	xxx
XXXX	X	DDMONYYYY	XXXXXX	XXXXXXXXXX	XXXXXXXXXX	DDMONYYYY / DDMONYYYY	XXXXXX	XXXXXX	XXXXXX	X	X	xxx	xxx	xxx	xxx
	X	DDMONYYYY	XXXXXX	XXXXXXXXXX	XXXXXXXXXX	DDMONYYYY / DDMONYYYY	XXXXXX	XXXXXX	XXXXXX	X	X	xxx	xxx	xxx	xxx

Source: XXXX.SAS, Run on DDMMYYYY

Listing 55) Adverse events related to Ipilimumab

POPULATION: SAF

Patient Number	AE #	Date on which the investigat or finds out of the event (DDMMYYYY)	Description of event	Preferred Term	SOC	Start Date (DDMMYYYY) / End Date (DDMMYYYY)	Causality	Ongoing ?	Related to	SAE	AE SI	Grade	Outcome	Action taken	Trt. Req.?
XXXXX	X	DDMONYYYY	XXXXXX	XXXXXXXXX	XXXXXXXXX X	DDMONYYYY / DDMONYYYY	XXXXXX	XXXXXX	XXXXXX	X	X	xxx	xxx	xxx	xxx
	X	DDMONYYYY	XXXXXX	XXXXXXXXX	XXXXXXXXX X	DDMONYYYY / DDMONYYYY	XXXXXX	XXXXXX	XXXXXX	X	X	xxx	xxx	xxx	xxx
	X	DDMONYYYY	XXXXXX	XXXXXXXXX	XXXXXXXXX X	DDMONYYYY / DDMONYYYY	XXXXXX	XXXXXX	XXXXXX	X	X	xxx	xxx	xxx	xxx
	X	DDMONYYYY	XXXXXX	XXXXXXXXX	XXXXXXXXX X	DDMONYYYY / DDMONYYYY	XXXXXX	XXXXXX	XXXXXX	X	X	xxx	xxx	xxx	xxx
XXXX	X	DDMONYYYY	XXXXXX	XXXXXXXXX	XXXXXXXXX X	DDMONYYYY / DDMONYYYY	XXXXXX	XXXXXX	XXXXXX	X	X	xxx	xxx	xxx	xxx
	X	DDMONYYYY	XXXXXX	XXXXXXXXX	XXXXXXXXX X	DDMONYYYY / DDMONYYYY	XXXXXX	XXXXXX	XXXXXX	X	X	xxx	xxx	xxx	xxx

Source: XXXX.SAS, Run on DDMMYYYY

Listing 56) Adverse events related to Nivolumab

POPULATION: SAF

Patient Number	AE #	Date on which the investigation or finds out of the event (DDMMYYYY)	Description of event	Preferred Term	SOC	Start Date (DDMMYYYY) / End Date (DDMMYYYY)	Causality	Ongoing ?	Related to	SAE	AESI	Grade	Outcome	Action taken	Trt. Req.?
XXXXX	X	DDMMYYYY	XXXXXX	XXXXXXXX	XXXXXXXX X	DDMMYYYY / DDMMYYYY	XXXXXX	XXXXXX	XXXXXX	X	X	xxx	xxx	xxx	xxx
	X	DDMMYYYY	XXXXXX	XXXXXXXX	XXXXXXXX X	DDMMYYYY / DDMMYYYY	XXXXXX	XXXXXX	XXXXXX	X	X	xxx	xxx	xxx	xxx
	X	DDMMYYYY	XXXXXX	XXXXXXXX	XXXXXXXX X	DDMMYYYY / DDMMYYYY	XXXXXX	XXXXXX	XXXXXX	X	X	xxx	xxx	xxx	xxx
	X	DDMMYYYY	XXXXXX	XXXXXXXX	XXXXXXXX X	DDMMYYYY / DDMMYYYY	XXXXXX	XXXXXX	XXXXXX	X	X	xxx	xxx	xxx	xxx
XXXX	X	DDMMYYYY	XXXXXX	XXXXXXXX	XXXXXXXX X	DDMMYYYY / DDMMYYYY	XXXXXX	XXXXXX	XXXXXX	X	X	xxx	xxx	xxx	xxx
	X	DDMMYYYY	XXXXXX	XXXXXXXX	XXXXXXXX X	DDMMYYYY / DDMMYYYY	XXXXXX	XXXXXX	XXXXXX	X	X	xxx	xxx	xxx	xxx

Source: XXXX.SAS, Run on DDMMYYYY

Listing 57) Adverse events related to Combo Immuno Therapy

POPULATION: SAF

Patient Number	AE #	Date on which the investigation or finds out of the event (DDMMYYYY)	Description of event	Preferred Term	SOC	Start Date (DDMMYYYY) / End Date (DDMMYYYY)	Causality	Ongoing ?	Related to	SAE	AESI	Grade	Outcome	Action taken	Trt. Req.?
XXXXX	X	DDMONYYYY	XXXXXX	XXXXXXXXXX	XXXXXXXXXX	DDMONYYYY / DDMONYYYY	XXXXXX	XXXXXX	XXXXXX	X	X	xxx	xxx	xxx	xxx
	X	DDMONYYYY	XXXXXX	XXXXXXXXXX	XXXXXXXXXX	DDMONYYYY / DDMONYYYY	XXXXXX	XXXXXX	XXXXXX	X	X	xxx	xxx	xxx	xxx
	X	DDMONYYYY	XXXXXX	XXXXXXXXXX	XXXXXXXXXX	DDMONYYYY / DDMONYYYY	XXXXXX	XXXXXX	XXXXXX	X	X	xxx	xxx	xxx	xxx
	X	DDMONYYYY	XXXXXX	XXXXXXXXXX	XXXXXXXXXX	DDMONYYYY / DDMONYYYY	XXXXXX	XXXXXX	XXXXXX	X	X	xxx	xxx	xxx	xxx
XXXX	X	DDMONYYYY	XXXXXX	XXXXXXXXXX	XXXXXXXXXX	DDMONYYYY / DDMONYYYY	XXXXXX	XXXXXX	XXXXXX	X	X	xxx	xxx	xxx	xxx
	X	DDMONYYYY	XXXXXX	XXXXXXXXXX	XXXXXXXXXX	DDMONYYYY / DDMONYYYY	XXXXXX	XXXXXX	XXXXXX	X	X	xxx	xxx	xxx	xxx

Source: XXXX.SAS, Run on DDMMYYYY

Listing 58) Adverse events related to LGX818

POPULATION: SAF

Patient Number	AE#	Date on which the investigator finds out of the event (DDMMYYYY)	Description of event	Preferred Term	SOC	Start Date (DDMMYYYY) / End Date (DDMMYYYY)	Causality	Ongoing?	Related to	SAE	AESI	Grade	Outcome	Action taken	Trt. Req.?
XXXXX	X	DDMMYYYY	XXXXXX	XXXXXXXX	XXXXXXXX	DDMMYYYY / DDMMYYYY	XXXXXX	XXXXXX	XXXXXX	X	X	xxx	xxx	xxx	xxx
	X	DDMMYYYY	XXXXXX	XXXXXXXX	XXXXXXXX	DDMMYYYY / DDMMYYYY	XXXXXX	XXXXXX	XXXXXX	X	X	xxx	xxx	xxx	xxx
	X	DDMMYYYY	XXXXXX	XXXXXXXX	XXXXXXXX	DDMMYYYY / DDMMYYYY	XXXXXX	XXXXXX	XXXXXX	X	X	xxx	xxx	xxx	xxx
	X	DDMMYYYY	XXXXXX	XXXXXXXX	XXXXXXXX	DDMMYYYY / DDMMYYYY	XXXXXX	XXXXXX	XXXXXX	X	X	xxx	xxx	xxx	xxx
XXXX	X	DDMMYYYY	XXXXXX	XXXXXXXX	XXXXXXXX	DDMMYYYY / DDMMYYYY	XXXXXX	XXXXXX	XXXXXX	X	X	xxx	xxx	xxx	xxx
	X	DDMMYYYY	XXXXXX	XXXXXXXX	XXXXXXXX	DDMMYYYY / DDMMYYYY	XXXXXX	XXXXXX	XXXXXX	X	X	xxx	xxx	xxx	xxx

Source: XXXX.SAS, Run on DDMMYYYY

Listing 59) Adverse events related to MEK162

POPULATION: SAF

Patient Number	AE #	Date on which the investigation or finds out of the event (DDMMYYYY)	Description of event	Preferred Term	SOC	Start Date (DDMMYYYY) / End Date (DDMMYYYY)	Causality	Ongoing ?	Related to	SAE	AESI	Grade	Outcome	Action taken	Trt. Req.?
XXXXX	X	DDMONYYYY	XXXXXX	XXXXXXXXXX	XXXXXXXXXX X	DDMONYYYY / DDMONYYYY	XXXXXX	XXXXXX	XXXXXX	X	X	xxx	xxx	xxx	xxx
	X	DDMONYYYY	XXXXXX	XXXXXXXXXX	XXXXXXXXXX X	DDMONYYYY / DDMONYYYY	XXXXXX	XXXXXX	XXXXXX	X	X	xxx	xxx	xxx	xxx
	X	DDMONYYYY	XXXXXX	XXXXXXXXXX	XXXXXXXXXX X	DDMONYYYY / DDMONYYYY	XXXXXX	XXXXXX	XXXXXX	X	X	xxx	xxx	xxx	xxx
	X	DDMONYYYY	XXXXXX	XXXXXXXXXX	XXXXXXXXXX X	DDMONYYYY / DDMONYYYY	XXXXXX	XXXXXX	XXXXXX	X	X	xxx	xxx	xxx	xxx
XXXX	X	DDMONYYYY	XXXXXX	XXXXXXXXXX	XXXXXXXXXX X	DDMONYYYY / DDMONYYYY	XXXXXX	XXXXXX	XXXXXX	X	X	xxx	xxx	xxx	xxx
	X	DDMONYYYY	XXXXXX	XXXXXXXXXX	XXXXXXXXXX X	DDMONYYYY / DDMONYYYY	XXXXXX	XXXXXX	XXXXXX	X	X	xxx	xxx	xxx	xxx

Source: XXXX.SAS, Run on DDMMYYYY

Listing 60) Adverse events related to Combo Target Therapy

POPULATION: SAF

Patient Number	AE #	Date on which the investigator finds out of the event (DDMMYYYY)	Description of event	Preferred Term	SOC	Start Date (DDMMYYYY) / End Date (DDMMYYYY)	Causality	Ongoing ?	Related to	SAE	AESI	Grade	Outcome	Action taken	Trt. Req. ?
XXXXX	X	DDMONYYYY	XXXXXX	XXXXXXXXXX	XXXXXX	DDMONYYYY / DDMONYYYY	XXXXXX	XXXXXX	XXXXXX	X	X	xxx	xxx	xxx	xxx
	X	DDMONYYYY	XXXXXX	XXXXXXXXXX	XXXXXX	DDMONYYYY / DDMONYYYY	XXXXXX	XXXXXX	XXXXXX	X	X	xxx	xxx	xxx	xxx
	X	DDMONYYYY	XXXXXX	XXXXXXXXXX	XXXXXX	DDMONYYYY / DDMONYYYY	XXXXXX	XXXXXX	XXXXXX	X	X	xxx	xxx	xxx	xxx
	X	DDMONYYYY	XXXXXX	XXXXXXXXXX	XXXXXX	DDMONYYYY / DDMONYYYY	XXXXXX	XXXXXX	XXXXXX	X	X	xxx	xxx	xxx	xxx
XXXX	X	DDMONYYYY	XXXXXX	XXXXXXXXXX	XXXXXX	DDMONYYYY / DDMONYYYY	XXXXXX	XXXXXX	XXXXXX	X	X	xxx	xxx	xxx	xxx
	X	DDMONYYYY	XXXXXX	XXXXXXXXXX	XXXXXX	DDMONYYYY / DDMONYYYY	XXXXXX	XXXXXX	XXXXXX	X	X	xxx	xxx	xxx	xxx

Source: XXXX.SAS, Run on DDMMYYYY

Listing 61) Serious Adverse events

POPULATION: SAF

Patient Number	AE #	Date on which the investigation or finds out of the event (DDMMYYYY)	Description of event	Preferred Term	SOC	Start Date (DDMMYYYY) / End Date (DDMMYYYY)	Causality	Ongoing ?	Related to	SAE	AESI	Grade	Outcome	Action taken	Trt. Req.?
XXXXX	X	DDMONYYYY	XXXXXX	XXXXXXXXX	XXXXXXXXX X	DDMONYYYY / DDMONYYYY	XXXXXX	XXXXXX	XXXXXX	X	X	xxx	xxx	xxx	xxx
	X	DDMONYYYY	XXXXXX	XXXXXXXXX	XXXXXXXXX X	DDMONYYYY / DDMONYYYY	XXXXXX	XXXXXX	XXXXXX	X	X	xxx	xxx	xxx	xxx
	X	DDMONYYYY	XXXXXX	XXXXXXXXX	XXXXXXXXX X	DDMONYYYY / DDMONYYYY	XXXXXX	XXXXXX	XXXXXX	X	X	xxx	xxx	xxx	xxx
	X	DDMONYYYY	XXXXXX	XXXXXXXXX	XXXXXXXXX X	DDMONYYYY / DDMONYYYY	XXXXXX	XXXXXX	XXXXXX	X	X	xxx	xxx	xxx	xxx
XXXX	X	DDMONYYYY	XXXXXX	XXXXXXXXX	XXXXXXXXX X	DDMONYYYY / DDMONYYYY	XXXXXX	XXXXXX	XXXXXX	X	X	xxx	xxx	xxx	xxx
	X	DDMONYYYY	XXXXXX	XXXXXXXXX	XXXXXXXXX X	DDMONYYYY / DDMONYYYY	XXXXXX	XXXXXX	XXXXXX	X	X	xxx	xxx	xxx	xxx

Source: XXXX.SAS, Run on DDMMYYYY

Listing 62) Adverse events leading to death

POPULATION: SAF

Patient Number	AE #	Date on which the investigation or finds out of the event (DDMMYYYY)	Description of event	Preferred Term	SOC	Start Date (DDMMYYYY) / End Date (DDMMYYYY)	Causality	Ongoing ?	Related to	SAE	AESI	Grade	Outcome	Action taken	Trt. Req.?
XXXXX	X	DDMMYYYY	XXXXXX	XXXXXXXX	XXXXXXXX X	DDMMYYYY / DDMMYYYY	XXXXXX	XXXXXX	XXXXXX	X	X	xxx	xxx	xxx	xxx
	X	DDMMYYYY	XXXXXX	XXXXXXXX	XXXXXXXX X	DDMMYYYY / DDMMYYYY	XXXXXX	XXXXXX	XXXXXX	X	X	xxx	xxx	xxx	xxx
	X	DDMMYYYY	XXXXXX	XXXXXXXX	XXXXXXXX X	DDMMYYYY / DDMMYYYY	XXXXXX	XXXXXX	XXXXXX	X	X	xxx	xxx	xxx	xxx
	X	DDMMYYYY	XXXXXX	XXXXXXXX	XXXXXXXX X	DDMMYYYY / DDMMYYYY	XXXXXX	XXXXXX	XXXXXX	X	X	xxx	xxx	xxx	xxx
XXXX	X	DDMMYYYY	XXXXXX	XXXXXXXX	XXXXXXXX X	DDMMYYYY / DDMMYYYY	XXXXXX	XXXXXX	XXXXXX	X	X	xxx	xxx	xxx	xxx
	X	DDMMYYYY	XXXXXX	XXXXXXXX	XXXXXXXX X	DDMMYYYY / DDMMYYYY	XXXXXX	XXXXXX	XXXXXX	X	X	xxx	xxx	xxx	xxx

Source: XXXX.SAS, Run on DDMMYYYY

Listing 63) Adverse events leading to hospitalization

POPULATION: SAF

Patient Number	AE#	Date on which the investigator finds out of the event (DDMMYYYY)	Description of event	Preferred Term	SOC	Start Date (DDMMYYYY) / End Date (DDMMYYYY)	Causality	Ongoing?	Related to	SAE	AESI	Grade	Outcome	Action taken	Trt. Req.?
XXXXX	X	DDMMYYYY	XXXXXX	XXXXXXXX	XXXXXXXX	DDMMYYYY / DDMMYYYY	XXXXXX	XXXXXX	XXXXXX	X	X	xxx	xxx	xxx	xxx
	X	DDMMYYYY	XXXXXX	XXXXXXXX	XXXXXXXX	DDMMYYYY / DDMMYYYY	XXXXXX	XXXXXX	XXXXXX	X	X	xxx	xxx	xxx	xxx
	X	DDMMYYYY	XXXXXX	XXXXXXXX	XXXXXXXX	DDMMYYYY / DDMMYYYY	XXXXXX	XXXXXX	XXXXXX	X	X	xxx	xxx	xxx	xxx
	X	DDMMYYYY	XXXXXX	XXXXXXXX	XXXXXXXX	DDMMYYYY / DDMMYYYY	XXXXXX	XXXXXX	XXXXXX	X	X	xxx	xxx	xxx	xxx
XXXX	X	DDMMYYYY	XXXXXX	XXXXXXXX	XXXXXXXX	DDMMYYYY / DDMMYYYY	XXXXXX	XXXXXX	XXXXXX	X	X	xxx	xxx	xxx	xxx
	X	DDMMYYYY	XXXXXX	XXXXXXXX	XXXXXXXX	DDMMYYYY / DDMMYYYY	XXXXXX	XXXXXX	XXXXXX	X	X	xxx	xxx	xxx	xxx

Source: XXXX.SAS, Run on DDMMYYYY

Listing 64) Adverse events leading to study withdrawal

POPULATION: SAF

Patient Number	AE #	Date on which the investigation or finds out of the event (DDMMYYYY)	Description of event	Preferred Term	SOC	Start Date (DDMMYYYY) / End Date (DDMMYYYY)	Causality	Ongoing ?	Related to	SAE	AESI	Grade	Outcome	Action taken	Trt. Req.?
XXXXX	X	DDMONYYYY	XXXXXX	XXXXXXXXXX	XXXXXXXXXX X	DDMONYYYY / DDMONYYYY	XXXXXX	XXXXXX	XXXXXX	X	X	xxx	xxx	xxx	xxx
	X	DDMONYYYY	XXXXXX	XXXXXXXXXX	XXXXXXXXXX X	DDMONYYYY / DDMONYYYY	XXXXXX	XXXXXX	XXXXXX	X	X	xxx	xxx	xxx	xxx
	X	DDMONYYYY	XXXXXX	XXXXXXXXXX	XXXXXXXXXX X	DDMONYYYY / DDMONYYYY	XXXXXX	XXXXXX	XXXXXX	X	X	xxx	xxx	xxx	xxx
	X	DDMONYYYY	XXXXXX	XXXXXXXXXX	XXXXXXXXXX X	DDMONYYYY / DDMONYYYY	XXXXXX	XXXXXX	XXXXXX	X	X	xxx	xxx	xxx	xxx
XXXX	X	DDMONYYYY	XXXXXX	XXXXXXXXXX	XXXXXXXXXX X	DDMONYYYY / DDMONYYYY	XXXXXX	XXXXXX	XXXXXX	X	X	xxx	xxx	xxx	xxx
	X	DDMONYYYY	XXXXXX	XXXXXXXXXX	XXXXXXXXXX X	DDMONYYYY / DDMONYYYY	XXXXXX	XXXXXX	XXXXXX	X	X	xxx	xxx	xxx	xxx

Source: XXXX.SAS, Run on DDMMYYYY

Listing 65) Adverse events of special interest (AESI)

POPULATION: SAF

Patient Number	AE #	Date on which the investigation or finds out of the event (DDMMYYYY)	Description of event	Preferred Term	SOC	Start Date (DDMMYYYY) / End Date (DDMMYYYY)	Causality	Ongoing ?	Related to	SAE	AESI	Grade	Outcome	Action taken	Trt. Req.?
XXXXX	X	DDMONYYYY	XXXXXX	XXXXXXXXX	XXXXXXXXX X	DDMONYYYY / DDMONYYYY	XXXXXX	XXXXXX	XXXXXX	X	X	xxx	xxx	xxx	xxx
	X	DDMONYYYY	XXXXXX	XXXXXXXXX	XXXXXXXXX X	DDMONYYYY / DDMONYYYY	XXXXXX	XXXXXX	XXXXXX	X	X	xxx	xxx	xxx	xxx
	X	DDMONYYYY	XXXXXX	XXXXXXXXX	XXXXXXXXX X	DDMONYYYY / DDMONYYYY	XXXXXX	XXXXXX	XXXXXX	X	X	xxx	xxx	xxx	xxx
	X	DDMONYYYY	XXXXXX	XXXXXXXXX	XXXXXXXXX X	DDMONYYYY / DDMONYYYY	XXXXXX	XXXXXX	XXXXXX	X	X	xxx	xxx	xxx	xxx
XXXX	X	DDMONYYYY	XXXXXX	XXXXXXXXX	XXXXXXXXX X	DDMONYYYY / DDMONYYYY	XXXXXX	XXXXXX	XXXXXX	X	X	xxx	xxx	xxx	xxx
	X	DDMONYYYY	XXXXXX	XXXXXXXXX	XXXXXXXXX X	DDMONYYYY / DDMONYYYY	XXXXXX	XXXXXX	XXXXXX	X	X	xxx	xxx	xxx	xxx

Source: XXXX.SAS, Run on DDMMYYYY

Listing 66) Prior Medications

POPULATION: ITT

Site	Patient Number	CM (#)	Drug	Generic name	3 rd level ATC subgroup	Dose	Unit	Start Date (DDMMYYYY)	End Date (DDMMYYYY)	Ongoing?	Route	Frequency	Indication	AE #
XXX	XXXXXXXX	XXX	XXXXXXXX	XXXX	XXX	XXX	XX X	DDMMYYYY	DDMMYYYY	XXX	XXX	XXX	XXX	XXX
XXX	XXXXXXXX	XXX	XXXXXXXX	XXXX	XXX	XXX	XX X	DDMMYYYY	DDMMYYYY	XXX	XXX	XXX	XXX	XXX
XXX	XXXXXXXX	XXX	XXXXXXXX	XXXX	XXX	XXX	XX X	DDMMYYYY	DDMMYYYY	XXX	XXX	XXX	XXX	XXX
XXX	XXXXXXXX	XXX	XXXXXXXX	XXXX	XXX	XXX	XX X	DDMMYYYY	DDMMYYYY	XXX	XXX	XXX	XXX	XXX

Notes:

Prior Medications were coded using the WHO-DRL Version XXXX.

CD = Drug prescribed for concomitant disease, P = Drugs administered prophylactically, AEn = Number of corresponding AE.

Prior medications are those which stopped prior to the first dose of study medication.

Source: XXXX.SAS, Run on DDMMYYYY

Listing 67) Concomitant Medications

POPULATION: ITT

Site	Patient Number	CM (#)	Drug	Generic name	3 rd level ATC subgroup	Dose	Unit	Start Date (DDMMYYYY)	End Date (DDMMYYYY)	Ongoing?	Route	Frequency	Indication	AE #
XXX	XXXXXXXX	XXX	XXXXXXXX	XXXX	XXX	XXX	XXX	DDMMYYYY	DDMMYYYY	XXX	XXX	XXX	XXX	XXX
XXX	XXXXXXXX	XXX	XXXXXXXX	XXXX	XXX	XXX	XXX	DDMMYYYY	DDMMYYYY	XXX	XXX	XXX	XXX	XXX
XXX	XXXXXXXX	XXX	XXXXXXXX	XXXX	XXX	XXX	XXX	DDMMYYYY	DDMMYYYY	XXX	XXX	XXX	XXX	XXX
XXX	XXXXXXXX	XXX	XXXXXXXX	XXXX	XXX	XXX	XXX	DDMMYYYY	DDMMYYYY	XXX	XXX	XXX	XXX	XXX

Notes:

Concomitant Medications were coded using the WHO-DRL Version XXXX.

CD = Drug prescribed for concomitant disease, P = Drugs administered prophylactically, AEn = Number of corresponding AE.

Concomitant Medications are those medications which:

started prior to, on or after the first dose of study medication and started no later than date of last study dose,
 AND

ended on or after the date of first dose of study medication or were ongoing at the end of the study.

Source: XXXX.SAS, Run on DDMMYYYY

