4.3. DESCRIPTION OF TREATMENTS

The following IMPs will be used in the study:

- Arm A: Combo Target (LGX818 450 mg p.o. od + MEK162 45 mg p.o. bid) until PD; then Combo Immuno (nivolumab 1 mg/kg solution i.v.combined with ipilimumab 3 mg/kg solution i.v.every 3 weeks for 4 doses then nivolumab 3 mg/kg solution i.v.every 2 weeks) until PD.
- Arm B: Combo Immuno (nivolumab 1 mg/kg solution i.v.combined with ipilimumab 3 mg/kg solution i.v.every 3 weeks for 4 doses then nivolumab 3 mg/kg solution i.v.every 2 weeks) until PD; then Combo Target (LGX818 450 mg p.o. od + MEK162 45 mg p.o. bid) until PD.
- Arm C: Combo Target (LGX818 450 mg p.o. od + MEK162 45 mg p.o. bid) for 8 weeks followed by Combo Immuno (nivolumab 1 mg/kg solution i.v.combined with ipilimumab 3 mg/kg solution i.v.every 3 weeks for 4 doses then nivolumab 3 mg/kg solution i.v.every 2 weeks) until PD; then Combo Target (LGX818 450 mg p.o. od + MEK162 45 mg p.o. bid) until PD.

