9.3. MISSING DATA

Any Missing data will not be imputed (including efficacy data).

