21.1. ADVERSE EVENTS

All adverse events (AEs) reported on eCRF and experienced by the patient on or after the informed consent date will be considered in the analysis. Thus, there will not be derivation to Treatment-emerged Adverse Events (TEAE) and not TEAE.

Adverse event Investigator terms will be assigned to a Preferred Term (PT) and will be classified by primary System Organ Class (SOC) according to the Medical Dictionary for Regulatory Activities (MedDRA) thesaurus, version 20.0 or higher

Counts and percentages will be presented by primary System Organ Class (SOC) and Preferred Term (PT) as defined in MedDRA thesaurus, by treatment arm.

A patient having more than one AE with the same PT will be counted only once in the incidence calculation for that PT. Similarly, if a patient has more than one AE in the same SOC, the patient will be counted only once in the total number of patients with an AE for that SOC.

An AE will be defined “Related” if causality is “Certain”, “Probable” or “Possible”.

The following frequency distributions of adverse events will be provided by treatment arm:

- An overview of AEs including the number of patients with:
 - at least one AE,
 - at least one non-serious AE,
 - at least one AE related to Ipilimumab,
 - at least one AE related to Nivolumab,
 - at least one AE related to Combo Immuno Therapy,
 - at least one AE related to LGX818,
 - at least one AE related to MEK162,
 - at least one AE related to Combo Target Therapy,
 - at least one serious AE (SAE),
 - at least one SAE related to Ipilimumab,
 - at least one SAE related to Nivolumab,
 - at least one SAE related to Combo Immuno Therapy,
 - at least one SAE related to LGX818,
 - at least one SAE related to MEK162,
 - at least one SAE related to Combo Target Therapy,
 - at least one AE leading to hospitalization,
 - at least one AE leading to withdrawal from the study,

- at least on AESI,
and the number of AEs, non-serious AEs, SAEs, AEs related to Ipilimumab, AEs related to Nivolumab, AEs related to Combo Immuno Therapy, AEs related to LGX818, AEs related to MEK162, AEs related to Combo Target Therapy, SAEs related to Ipilimumab, SAEs related to Nivolumab, SAEs related to Combo Immuno Therapy, SAEs related to LGX818, SAEs related to MEK162, SAEs related to Combo Target Therapy, AEs leading to hospitalization, AEs leading to death, AEs leading to study withdrawal, AESIs;
- AEs presented by Primary SOC and PT;

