Number of SAEs related to Combo LGX818	n	xx	xx	xx
Number of SAEs related to Combo MEK162	n	xx	xx	xx
Number of SAEs related to Combo Target Therapy	n	xx	xx	xx
Number of AEs leading to hospitalization	n	xx	xx	xx
Number of AEs leading to death	n	xx	xx	xx
Number of AEs leading to withdrawal from the study	n	xx	xx	xx
Number of AEs of special interest (AESI)	n	xx	xx	xx
Number of Patients with at Least One AE	n (%)	xx (xx.x%)	xx (xx.x%)	xx (xx.x%)
Number of Patients with at Least One non-serious AE	n (%)	xx (xx.x%)	xx (xx.x%)	xx (xx.x%)
Number of Patients with at Least One AE related to Ipilimumab	n (%)	xx (xx.x%)	xx (xx.x%)	xx (xx.x%)
Number of Patients with at Least One AE related to Nivolumab	n (%)	xx (xx.x%)	xx (xx.x%)	xx (xx.x%)
Number of Patients with at Least One AE related to Combo Immuno Therapy	n (%)	xx (xx.x%)	xx (xx.x%)	xx (xx.x%)
Number of Patients with at Least One AE related to LGX818	n (%)	xx (xx.x%)	xx (xx.x%)	xx (xx.x%)
Number of Patients with at Least One AE related to MEK162	n (%)	xx (xx.x%)	xx (xx.x%)	xx (xx.x%)
Number of Patients with at Least One AE related to Combo Target Therapy	n (%)	xx (xx.x%)	xx (xx.x%)	xx (xx.x%)
Number of Patients with at Least One serious AE (SAE)	n (%)	xx (xx.x%)	xx (xx.x%)	xx (xx.x%)
Number of Patients with at Least One SAE related to Ipilimumab	n (%)	xx (xx.x%)	xx (xx.x%)	xx (xx.x%)
Number of Patients with at Least One SAE related to Nivolumab	n (%)	xx (xx.x%)	xx (xx.x%)	xx (xx.x%)
Number of Patients with at Least One SAE related to Combo Immuno Therapy	n (%)	xx (xx.x%)	xx (xx.x%)	xx (xx.x%)
Number of Patients with at Least One SAE related to Combo LGX818	n (%)	xx (xx.x%)	xx (xx.x%)	xx (xx.x%)
Number of Patients with at Least One SAE related to Combo MEK162	n (%)	xx (xx.x%)	xx (xx.x%)	xx (xx.x%)
Number of Patients with at Least One SAE related to Combo Target Therapy	n (%)	xx (xx.x%)	xx (xx.x%)	xx (xx.x%)
Number of Patients with at Least One AE leading to hospitalization	n (%)	xx (xx.x%)	xx (xx.x%)	xx (xx.x%)
Number of Patients with at Least One AE leading to withdrawal from the study	n (%)	xx (xx.x%)	xx (xx.x%)	xx (xx.x%)
Number of Patients with at Least One AESI	n (%)	xx (xx.x%)	xx (xx.x%)	xx (xx.x%)

Note: a) Percentages are calculated relative to the total number of patients in the SAF population by treatment arm.

b) An AE is defined as "related" to a study drug if relationship is "Certain", "Probable" or "Possible" to that specific drug. Missing data were considered as Related.

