<PT>	n (%) E	xx (xx.x%) xx	xx (xx.x%) xx	xx (xx.x%) xx

Note: a) Percentages are calculated relative to the total number of patients in the SAF Population by treatment arm.
 b) Each patient is counted at most once within each SOC and PT.
 c) AEs were coded using MedDRA version XX.X.
 d) n = number of patients, E = number of events.
 e) An AE is "related" to a study drug if relationship is "Certain", "Probable" or "Possible". Missing data were considered as Related.

Source: XXXX.SAS, Run on DDMMYYYY

TABLE 48. Incidence of Nivolumab-related AEs by primary System Organ Class and Preferred Term

POPULATION: SAF

	Statistic	Arm A (N = XX)	Arm B (N = XX)	Arm C (N = XX)
<Primary SOC>	n (%) E	xx (xx.x%) xx	xx (xx.x%) xx	xx (xx.x%) xx
<PT>	n (%) E	xx (xx.x%) xx	xx (xx.x%) xx	xx (xx.x%) xx
<PT>	n (%) E	xx (xx.x%) xx	xx (xx.x%) xx	xx (xx.x%) xx
<PT>	n (%) E	xx (xx.x%) xx	xx (xx.x%) xx	xx (xx.x%) xx
<Primary SOC>	n (%) E	xx (xx.x%) xx	xx (xx.x%) xx	xx (xx.x%) xx
<PT>	n (%) E	xx (xx.x%) xx	xx (xx.x%) xx	xx (xx.x%) xx
<PT>	n (%) E	xx (xx.x%) xx	xx (xx.x%) xx	xx (xx.x%) xx
<PT>	n (%) E	xx (xx.x%) xx	xx (xx.x%) xx	xx (xx.x%) xx
<Primary SOC>	n (%) E	xx (xx.x%) xx	xx (xx.x%) xx	xx (xx.x%) xx
<PT>	n (%) E	xx (xx.x%) xx	xx (xx.x%) xx	xx (xx.x%) xx
<PT>	n (%) E	xx (xx.x%) xx	xx (xx.x%) xx	xx (xx.x%) xx
<PT>	n (%) E	xx (xx.x%) xx	xx (xx.x%) xx	xx (xx.x%) xx
<Primary SOC>	n (%) E	xx (xx.x%) xx	xx (xx.x%) xx	xx (xx.x%) xx
<PT>	n (%) E	xx (xx.x%) xx	xx (xx.x%) xx	xx (xx.x%) xx
<PT>	n (%) E	xx (xx.x%) xx	xx (xx.x%) xx	xx (xx.x%) xx
<PT>	n (%) E	xx (xx.x%) xx	xx (xx.x%) xx	xx (xx.x%) xx

Note: a) Percentages are calculated relative to the total number of patients in the SAF Population by treatment arm.
 b) Each patient is counted at most once within each SOC and PT.
 c) AEs were coded using MedDRA version XX.X.
 d) n = number of patients, E = number of events.
 e) An AE is "related" to a study drug if relationship is "Certain", "Probable" or "Possible". Missing data were considered as Related.

Source: XXXX.SAS, Run on DDMMYYYY

TABLE 49. Incidence of Combo Immuno Therapy-related AEs by primary System Organ Class and Preferred Term

POPULATION: SAF

	Statistic	Arm A (N = XX)	Arm B (N = XX)	Arm C (N = XX)
<Primary SOC>	n (%) E	xx (xx.x%) xx	xx (xx.x%) xx	xx (xx.x%) xx
<PT>	n (%) E	xx (xx.x%) xx	xx (xx.x%) xx	xx (xx.x%) xx
<PT>	n (%) E	xx (xx.x%) xx	xx (xx.x%) xx	xx (xx.x%) xx
<PT>	n (%) E	xx (xx.x%) xx	xx (xx.x%) xx	xx (xx.x%) xx

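### Counting missing causality as related, with no check on exposure, could charge adverse events to drugs the patient has not yet received

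*Supplement*

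**What the plan says.** Table and listing numbers here are those printed on the shells; the list of shells at the start of SAP section 26 numbers these tables two lower.

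- **Shells.** Note b of Table 45 (the AE overview) ties relatedness to the individual drug and then deals with blanks: "to that specific drug. Missing data were considered as Related". Note e of Tables 47 to 52 (ipilimumab, nivolumab, Combo Immuno, LGX818, MEK162, Combo Target) repeats it: "Missing data were considered as Related". Each table has columns for Arms A, B and C, with percentages based on all safety-set patients in the arm.
- **Section 21.1.** The definition in the text uses three causality grades and does not mention missing values: "An AE will be defined “Related” if causality is “Certain”, “Probable” or “Possible". All events "experienced by the patient on or after the informed consent date will be considered in the analysis", and "there will not be derivation to Treatment-emerged Adverse Events (TEAE) and not TEAE".
- **Section 9.3.** The general rule is "Any Missing data will not be imputed (including efficacy data").
- **Section 4.3.** Arm A is described as "Arm A: Combo Target (LGX818 450 mg p.o. od + MEK162 45 mg p.o. bid) until PD; then Combo Immuno". Arm B starts with Combo Immuno, given "until PD; then Combo Target (LGX818 450 mg p.o. od + MEK162 45 mg p.o. bid) until PD". Arm C has 8 weeks of Combo Target before any immunotherapy.

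**The concern.** Treating unknown causality as related is a familiar cautious convention when every patient is already on the drug in question. Here most patients spend their first treatment block on only one of the two combinations. For an event in that block, or between consent and first dose, being related to the other combination is impossible rather than uncertain. A rule that nevertheless counts it as related is misattributing, not being cautious.

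The direction of the error depends on the arm: towards immunotherapy in Arm A and in the Arm C lead-in, and towards targeted therapy in Arm B. Toxicity of the study drugs is both a secondary and a safety objective (sections 3.2 and 3.3), and the drug-related tables are where a reader would compare the three sequences on it. A patient who never reaches the second combination stays in the denominator and could also enter the numerator for drugs never taken.

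There is also a plain inconsistency. A programmer working from sections 21.1 and 9.3 would leave an AE with missing causality out of the related counts. One working from the shells would put it in.

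**Working it through.** The plan gives no figure to reproduce, so the check is mainly of the text.

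**Does any rule stop the misattribution?**

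1. The shell notes carry no condition on exposure.
2. Section 21.1 takes events from consent onwards and derives no treatment-emergent status, so timing relative to dosing is not used to filter events.
3. The safety set (section 7) places patients by the drug actually received. That settles which arm column a patient falls in; it says nothing about exposure at the start of an event.
4. The denominator is the whole arm in the safety set, not the patients exposed to the drug.

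None of these prevents it. Read literally, a first-block AE with missing causality meets the shell definition of related for all four drugs, two of which have not been given. This follows from the absence of a restriction; the shells do not say it in words.

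**How large could it be?** The documents give neither the share of AEs with missing causality nor the number of AEs per patient. Suppose each patient has *k* AEs before the second combination starts, causality is missing independently for a share *m* of them, and each such AE is counted against every drug. The chance that a patient has at least one AE counted as related to a combination not yet received is

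1 − (1 − m)^k.

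For k = 10 and m = 1%: 1 − 0.99^10 = 0.096. The other values follow in the same way:

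| k (assumed) | m = 0% | m = 1% | m = 2% | m = 5% |
|---|---|---|---|---|
| 5 | 0% | 4.9% | 9.6% | 22.6% |
| 10 | 0% | 9.6% | 18.3% | 40.1% |
| 20 | 0% | 18.2% | 33.2% | 64.2% |

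With the 69 patients per arm of section 4.2, the k = 10 row corresponds to 0, 6.6, 12.6 and 27.7 patients.

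**With the exposure condition added**, the number counted against a not-yet-received drug through missing causality is 0 for every k and m, provided the order of the dates is known.

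**The case against.** Several points on the other side have force.

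- **The eCRF is not shown.** Listings 54 to 65 have one *Causality* column and one *Related to* column per AE. That layout fits a single grade plus a field naming the drug, in which case a missing grade might be charged only to the named drug. A listing can condense several fields, so this does not settle the matter, but it leaves the mechanism open.
- **Causality may never be missing.** Whether sites must complete it would normally be set outside the SAP. If it is always complete, the effect is nil.
- **Section 9.3 is not applied literally elsewhere.** Section 12.1 and Appendix 2 both complete partial dates, so the shell note could be read as added detail. The wording still conflicts, and section 21.1 still lacks the rule.
- **The reach is limited.** No between-arm tests are planned (section 8.3), and the all-AE and all-SAE tables (46 and 53) do not use relatedness. The AE listings show start dates and causality, so a wrong attribution could be traced.

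A reader might go further and infer that causality fields for drugs not yet started are blank by design, so that nearly every patient with a first-block AE would be counted. The documents do not support this. It needs a separate causality field for each drug with no option for not applicable; nothing shows such a form, and the listing layout, if anything, points the other way. Nor do the documents show that the tables will in fact be inflated, only that the rule allows it.

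**Conclusion.** The point stands in conditional form. As written, the shell rule can count an AE with missing causality as related to a drug the patient has not received. This is a stated rule that gives a wrong result in a sequential design, not merely a missing detail. The conflict with section 9.3 and the silence of section 21.1 need reconciling however much causality is missing.

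The size cannot be derived from the documents. The tabulated values rest on assumed AE counts, assumed missing rates, independence between AEs, and the reading that a blank counts against every drug. The consequence is confined to the descriptive related-AE and related-SAE tables; overall survival and the other efficacy analyses are untouched. It should be corrected before the tables are programmed, but it does not threaten the trial's main conclusion.

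**What to change.** In section 21.1, and in note b of Table 45 and note e of Tables 47 to 52, state that an AE with missing causality counts as related only to study drugs of which the patient had received at least one dose on or before the AE start date, and never to a drug not yet received. This also covers events before first dose. Name the rule as the exception to section 9.3. Listings 55 to 60, which select on relatedness, should use the same flag.

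Add a rule for partial AE start dates, since Appendix 2 covers medications only. For example, where the order of AE start and first dose cannot be determined, treat the drug as received only if the known part of the date is compatible with that.

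The cost is small: a few sentences in the SAP, one date derivation per drug and the partial-date rule. AE start dates (Listing 54) and therapy start dates (section 19) are already collected, so no new data are needed.
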